completed treatment. ***Following randomization of the schools to the intervention, there will be three waves of implementation: Wave 1 (1 school in 2019), Wave 2 (2 schools in 2019-2020), and Wave 3 (2 schools in 2020-2021).*** The 5 schools on the Fort Peck Reservation will be the clusters that are randomized to *NIE*. *NIE* will take approximately 40 weeks, or 3 quarters, to implement. The first observation period (Q4 of Year 2) provides baseline measurements for all respondents drawn from every cluster. The cluster is then surveyed at 3, 9, and 12 months for the students in the cluster once they have begun participation in the intervention, and at 9 and 12 months for the parents/legal guardians in the cluster once they have begun participation in the intervention. Following completion of the intervention across all clusters, we will conduct the quantitative analysis. The SWD allows us to control for the effect of time and ensure that the full AI population of schools at Fort Peck receives *NIE*. The systems-level component of *NIE* will be implemented reservation-wide rather than school-wide during Years 2 to 4 of *NIE* as the SWD is rolled out. The systems level component will be measured and analyzed qualitatively.

**2.3.6 Trial Timeline.** The timeline for *NIE* is: Year 1-Refine, tailor, and finalize the components of *NIE* with the CAB by reviewing our current quantitative and qualitative data from Fort Peck and by talking with elders

[figure not shown]

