**5.3.1. Data Collection Materials for Human Subjects.** For the individual-, family-, and community-level components of N/E, there are two forms of data collection: a student survey administered at baseline and at 3, 9, and 12 months after intervention inception, and a parent/legal guardian survey administered at baseline and at 9 and 12 months after intervention inception. The student survey will assess participation in Native Stand, Native Voices, and the cultural mentoring program. The parent survey will assess participation in Native Voices. [name] and the study's outreach coordinator will oversee the administration of the student surveys and the parent/legal guardian surveys. The student surveys and parent/legal guardian surveys will be completed utilizing REDCap. Between Years 2-4, 456 students and one of their parents or legal guardians will participate in N/E's data collection. Student surveys for baseline, 3 months, and 9 months will be administered to groups of 20 students at a time during regularly scheduled classes in an assigned classroom by [name] and the study's outreach coordinator. During data collection, groups of 20 students will be appropriately spaced in the classroom in order to ensure privacy, and survey instructions will be presented to students prior to REDCap administration. [name] and the study's outreach coordinator will thoroughly review the assent form with the students at the baseline data collection, which will include a description of N/E, types of questions that will be asked, and potential risks and benefits of participating in N/E. All students will be reminded that they can withdraw at any time without consequences. For students that graduate from high school prior to the 12 months data collection, they will be contacted by [name] directly to complete the 12 months data collection (during evening hours) at the high school they graduated from following the same procedure described above. This same procedure will be followed if the data collection time point occurs for some reason when school is not in session. The parent survey will be administered during evening hours at the high school in an assigned classroom by [name] and the study's outreach coordinator. We will use the same REDCap procedures for parents/legal guardians that are described for youth above. In addition, written consent will be obtained from the parents/legal guardians prior to their participation in the study. [name] and the study's outreach coordinator will review the informed consent with the parents/legal guardians at the time of data collection.

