Exclusion criteria are minimal due to the value the CAB places on inclusion in N/E's program implementation. Exclusion criteria include 1) not meeting the aforementioned inclusion criteria, and 2) having a physical or cognitive impairment that would impede the student's understanding of and participation in the content of Native Stand, Native Voices, and the cultural mentoring program. Study-enrolled students must agree at the outset to participate in Native Stand, Native Voices, and the cultural mentoring program, and agree to complete the survey at baseline and at 3, 9, and 12 months during and shortly after their cluster's program. Parents/legal guardians must also agree to participate in Native Voices and complete the parent/legal guardian survey at baseline and at 9 and 12 months. No persons will be coerced to engage in any study activity, and anyone may refuse to participate at any time. After written consent and assent are obtained from the parents/legal guardians and their children, respectively, they will be enrolled in the study. For inclusion in the systems-level component of the study, only those staff members who sit on the Epi Team as representatives of their respective agencies are eligible. Written informed consent will be obtained from the head of each agency represented on the Epi Team and the staff member participating in the Epi Team.

If at any point in the study a student discloses abuse, they will be referred to the appropriate person or organization. For example, a research participant who is under the age of 18 and in school who discloses that he or she is being abused at home will be referred to the counselors in the school for assistance, with the possibility of joint reporting to Child Protective Services. Students will be informed during the informed consent process that any abuse they may disclose will be reported, since the members of the research team and the interviewers are mandated reporters.

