
**Parent/Legal Guardian Survey.** The parent/legal guardian survey is based on parents'/legal guardians' participation in Native Voices. It includes a list of SRH topics about which the parent/legal guardian has spoken to the child and the frequency of times discussed. The parent/legal guardian measures have been validated in previous studies evaluating parent/child SRH communication and have been used by [name] in her Greenland studies. The SRH topic list and frequency is the same as in the student survey, only adapted for parents/legal guardians. Standard demographic measures included in the parent/legal guardian survey are age, gender, marital status, highest grade completed, and occupation.

**Barriers/Facilitators Discussion Guide.** The barriers/facilitators discussion guide is a qualitative assessment using open-ended questions that address the factors impeding and facilitating SRH services for AI youth on the Fort Peck Reservation. The guide is based on the 8 service domains for evidence-based clinical practices outlined in the CDC's Contraceptive and Reproductive Health Services for Teens: Evidence-based Clinical Best Practices Guide(80-82)-namely, contraceptive access; provision of hormonal contraception/IUD; emergency contraception; cervical cancer screening; STI/HIV/HCV testing and treatment; cost, confidentiality, consent; health center infrastructure; and health center environment.

**Coordination and Implementation Monitoring Plan Tracking Log.** The tracking log will monitor the progress toward completion of the 8 SRH service domains identified from the barriers/facilitators discussion

guide and corresponding evidence-based clinical practice elements.

**Focus Groups.** Data collection related to Aim 3 of our study, which is to evaluate the fidelity and acceptability of N/E, includes a focus group guide, as described above. The Aim 3 focus groups will include questions such as what experiences/activities they liked and/or did not like about the intervention, what educational information they did and/or did not like about the intervention, and what recommendations they have for improving the intervention.

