H1: AI youth who participate in N/E will demonstrate increased condom use at 3, 9, and 12 months. (12 months will be used in the Primary Outcome analysis; 3 and 9 months will be used in the Secondary Outcomes analysis.) H2: AI youth who participate in N/E will demonstrate increased use of other birth control at 3, 9, and 12 months. They also will demonstrate a decrease in sexual risk behaviors as measured by reduced number of sex partners, delayed onset of sexual intercourse, and decreased substance use during sex, at 3, 9, and 12 months. (Secondary Outcomes) H3: N/E parents/legal guardians and youth will demonstrate significantly increased communication about topics related to SRH at 3, 9, and 12 months. AI youth who participate in the cultural mentoring program will demonstrate significantly increased understanding of cultural values related to traditional AI beliefs regarding SRH at 3, 9, and 12 months. And AI youth who participate in N/E will report significantly increased use of SRH services at 3, 9, and 12 months as a result of improved coordination among education, health care, and social service agencies on the Fort Peck Reservation. (Tertiary Outcomes) AIM 3: Evaluate the fidelity and acceptability of N/E. N/E's fidelity and acceptability will be evaluated using qualitative methods, including focus groups, activity logs, and staff field notes and meetings.

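### The Trial Design text can be read as following up only people who have begun the intervention, and nothing says that enrolled non-starters are surveyed or analysed

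*Combined protocol and SAP*

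**What the plan says.** **Who is surveyed, and when.** Section 2.3.5 (Trial Design) says that the first observation period "provides baseline measurements for all respondents drawn from every cluster". It continues: "The cluster is then surveyed at 3, 9, and 12 months for the students in the cluster once they have begun participation in the intervention". Parents are surveyed "at 9 and 12 months for the parents/legal guardians in the cluster once they have begun participation in the intervention".

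Other sections run on a different clock. Section 5.3.1 (within Section 6) describes "a student survey administered at baseline and at 3, 9, and 12 months after intervention inception". Its enrolment text has students agree to "complete the survey at baseline and at 3, 9, and 12 months during and shortly after their cluster's program". Section 4.1 gives calendar times for Wave 1: students in December 2019, May/June 2020 and September 2020, and their parents in spring and fall 2020.

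**Hypotheses.** In the registration receipt and the progress report, H1 reads "AI youth who participate in N/E will demonstrate increased condom use at 3, 9, and 12 months". H2 is worded the same way. H3 is mixed. Its cultural-values part concerns youth in the mentoring program and its services part concerns youth who take part in N/E. Its communication part refers to N/E parents and youth with no such condition.

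**Analysis.** The model in Section 3.1.5 lets the intervention term be 0/1 or a dose. Section 3.1.3 builds dose from each student's attendance and participation. Section 3.1.2 imputes missing follow-ups from 3 to 12 months. The documents define no analysis population and do not state an intention-to-treat principle.

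**The concern.** Schools are randomised, and the only untreated survey described is the baseline one, given by everyone enrolled. Whether a person then starts a component is a choice made after randomisation. If that choice decides who gives a follow-up survey, the people measured change at the same moment as the exposure. Suppose those who engage already used condoms more, or already talked more with their child. The treated-minus-untreated difference would then be positive even if N/E did nothing. An exposure term built from attendance lets the same self-selection in by a second route, even if everyone is surveyed.

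**Working it through.** **1. The timing rules side by side.** Section 2.3.5 makes follow-up conditional on having begun. Its grammatical subject is the cluster, so the condition can be read as collective or individual. Sections 4.1 and 5.3.1 tie follow-up to the school, the wave, the calendar or the program's inception. They settle when surveys happen, but not whether an enrolled person who never starts is included.

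**2. The plan's own sample size.** Inputs from Section 3.1.1: Nu = 292, design effect 1.3273, attrition 15%, target 0.14, power 80%, significance level 0.05.

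- 292 × 1.3273 = 387.57
- 387.57 / 0.85 = 455.97, so 456

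The stated 456 reproduces. It allows for attrition and has no separate term for people who never start.

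**3. Students, participant-only reading, no true effect, nothing imputed.** Let f be the share of enrolled students who never start, and d the starter-minus-non-starter difference in condom-use proportion. Neither is in the documents. Baseline averages everyone and follow-up averages starters only:

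apparent change = m(starters) − [(1 − f) × m(starters) + f × m(non-starters)] = f × d

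The standard error implied by the plan's power, assuming a two-sided test (sidedness is not stated), is 0.14 / (1.96 + 0.84) = 0.050. The chance of rejecting is P(|Z + f × d / 0.050| > 1.96).

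| f | d | f × d | chance of rejecting (nominal 5%) |
|---|---|---|---|
| 0.05 | 0.20 | 0.010 | 5.5% |
| 0.10 | 0.20 | 0.020 | 6.9% |
| 0.15 | 0.20 | 0.030 | 9.2% |
| 0.15 | 0.30 | 0.045 | 14.7% |
| 0.30 | 0.30 | 0.090 | 43.7% |

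For d from 0.10 to 0.40, the shift runs from 0.015 to 0.060 at f = 0.15 and from 0.030 to 0.120 at f = 0.30. Producing the whole 0.14 would need d = 0.14 / 0.15 = 0.93 or d = 0.14 / 0.30 = 0.47 respectively.

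**4. Parents.** The same formula applies to the 24-item communication list in Table 2. Assume that 10% to 40% never attend and that non-attenders discuss 2 to 4 fewer topics. The shift is 0.10 × 2 = 0.2 to 0.40 × 4 = 1.6 topics, with a middle case of 0.25 × 3 = 0.75. The plan gives no target for this outcome to compare with.

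**5. Would imputation remove it?** Section 3.1.2 draws replacement values from observed respondents with similar propensity scores. Under the participant-only reading, every observed follow-up belongs to a starter. Matching could correct only what the propensity model captures, and the section itself expects attrition to be not missing at random. The sequence starts at 3 months, when parents have no survey. The text also does not say that a person never due a survey counts as missing.

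**The case against.** The best defence is that Section 2.3.5 need not be read individually. Its subject is the cluster, and Sections 4.1 and 5.3.1 consistently time surveys by school, wave or calendar. Section 4.1 also pursues graduates for the 12-month survey, which suggests an intent to follow everyone. Enrolled students agree at the outset to all components and surveys, and Native Stand is part of the regular class schedule, so few students should never start. All of this stands. A reader might infer that each person's own start date triggers the survey; the documents do not establish that. They leave the question open.

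A reader might also take "The parent/legal guardian survey is based on parents'/legal guardians' participation in Native Voices" to mean that only attenders are surveyed. The text that follows lists topics, so it describes content, and the same survey is given at baseline before any session. Nor are all three hypotheses conditional on participation: the communication part of H3, which is the parents' outcome, is not.

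On the analysis side, the exposure carries only cluster and period subscripts, so its 0/1 form is already at school level. The printed equation has only a school effect and a residual, but Section 3.1.5 says that the model class allows within-person autocorrelation. It is therefore too strong to say that the model must read selection as effect. It is also too strong to say that non-starters drop out of the treated data, since imputation is planned, though whether it covers them is not stated.

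Finally, a reader might attach a false-positive rate to the parent outcome. With an assumed SD of 6 and 15% other attrition, SE = 6 × √(1/456 + 1/(0.75 × 456 × 0.85)) = 0.45. The middle case of 0.75 topics would then reject about 38% of the time, and the whole grid about 8% to 91%. These rates are not supportable. Every input is invented, the SE treats two surveys of the same parents as independent, clustering is ignored, and the model's time effect is left out.

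**Conclusion.** The point holds as an ambiguity that should be closed because one of its readings admits bias. The documents do not say that enrolled non-starters are surveyed or analysed, most of the hypotheses are worded for participants, and an attendance-based exposure is left open for the primary model.

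The size and direction of any bias cannot be found from the documents. For the primary outcome, with 5% to 15% non-starters and a gap of 0.2, it is about 0.01 to 0.03, or 7% to 21% of the 0.14 target. That could raise the false-positive rate modestly but could not by itself produce the planned effect. The figures assume that non-starters are neither surveyed nor imputed, a plain before-and-after contrast, and the standard error implied by the stated power. The larger entries in the table need non-start rates that seem unlikely for students. The exposure is greater for parents and for the evening and mentoring components, where attendance is more a matter of choice.

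**What to change.** - **Section 2.3.5:** align the wording with Sections 4.1 and 5.3.1. State that all students enrolled at baseline are surveyed at 3, 9 and 12 months, and all enrolled parents at 9 and 12 months, after their school's wave starts, whether or not they begin any component.
- **Section 3.1.5 (mixed models):** set the primary exposure as 0/1 from the school's assigned wave for everyone enrolled at baseline, in place of the choice between 0/1 and dose.
- **H1 to H3:** word them for enrolled youth and parents.
- **Supportive analyses:** keep the dose and participants-only analyses, labelled as such.

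The cost is protocol and SAP wording plus a few extra surveys, using the same staff and incentives. The estimated effect will be somewhat smaller because people who never engaged are included.

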### **2.3.5 Trial Design.**

Our selection of an SWD to evaluate *NIE* is consistent with tribal members' desires that all 15- to 18-year-old AI youth receive the intervention. The SWD is a cluster-randomized trial, which involves random and sequential crossover of clusters from control to intervention until all clusters are exposed to the intervention. The first observation period corresponds to a baseline measurement observation, in which none of the clusters have been randomized to *NIE*.

Clusters are randomized to *NIE* at subsequent steps until all clusters have

*Nenunkumbi/Edahiyedo ("We Are Here Now"): A Multi-level, Multi-component Sexual and Reproductive Health Intervention for American Indian Youth*

**Figure 4. Trial design and timeline for implementing N/E relative to grant and sites/schools.**

*Nenunkumbi/Edahiyedo ("We Are Here Now"): A Multi-level, Multi-component Sexual and Reproductive Health Intervention for American Indian Youth*

and community stakeholders. We will have monthly team meetings and quarterly CAB meetings. When necessary, we will meet with CAB members individually. We will also recruit, hire, and train staff in *Native Stand* and *Native Voices*; identify the cultural mentors; purchase all necessary materials and supplies; finalize research protocols and IRB approvals. Years 2, 3, and 4- Collect baseline data; Implement *NIE*; conduct quantitative and qualitative data collection; conduct ongoing fidelity and acceptability data collection; and continue monthly team meetings and quarterly CAB meetings. Year 5-Finish data collection; conduct data analysis; work with CAB on interpretation of data analysis; develop sustainability plan; develop intervention toolkit; and disseminate results to scientific, professional, and Fort Peck communities. See Appendices for *NIE* timeline.

**2.3.7 Sample Size and Population.** *NIE*'s sample size is 456 AI male and female youth ages 15 to 18 years old. The population of AI youth 15 to 18-year-old attending the five schools participating in the study is approximately 617.

**2.3.8 Study Background and Rationale.** Comprehensive national surveillance data on SRH among AIs is difficult to assess due to the underrepresentation of AIs in national surveys. The data on AI SRH in the United States that are available demonstrate that AIs are disproportionately affected by adverse conditions attributable to SRH, compared to other populations. AI youth report earlier onset of sexual intercourse than other adolescent populations in the U.S. The teen birth rate among AIs is 2 to 3 times higher than that among Caucasians. In addition, the rates of pre-term birth and low birth weight are much higher in AIs compared to Caucasians. STIs are up to 4.6 times higher for AI males and females compared to Caucasians, with young AI males having the highest chlamydia rates of any racial- and age-specific population in the U.S. As a result, AI females have higher rates of miscarriages and ectopic pregnancies than Caucasian females and are at risk for infertility. For AI males, STIs can lead to urethritis, epididymitis, and prostate cancer, which is higher in AI men than all other racial and ethnic males in the U.S. In addition, the costly and burdensome health consequences of AI youths' high STI rates include infection with HIV and HCV. The incidence of HIV in AI males and females is 30% higher than in Caucasian males and females, and in recent years AIs are the only racial and ethnic group in which the incidence of HIV continues to rise. Furthermore, of all population subgroups in the U.S., the incidence of HCV is highest in AIs. At present no extant multi-level, multi-component intervention has been shown to be efficacious in addressing SRH among AI youth. The majority of AI interventions appearing in the peer-reviewed literature instead focus on alcohol and substance use reduction. Thus, a critical need exists to address the SRH disparities among AI youth, which place current and future generations of AI societies in jeopardy.

The literature related to SRH among AI youth identifies poverty, isolation, alcohol and other drug use, physical and sexual victimization, and lack of comprehensive and coordinated SRH education and clinical services as factors that influence unintended pregnancies and STIs. Evidence also suggests that ambivalence toward sex, social pressures, depression, anxiety, and experiences of historical trauma and loss influences sexual risk behavior among AIs. Mistrust of research and researchers continues in AI communities due to a legacy of neglect and betrayal by the U.S. government and by researchers from outside their communities. This mistrust impedes the cooperation between tribal communities and academics to design, implement, and evaluate effective interventions to address SRH disparities among AI youth.

The complex factors that influence sexual risk behaviors among AI youth warrant novel AI community-specific interventions. Previous research with AI youth on SRH has lacked an ecological design and implementation, and it has neither addressed nor leveraged the interconnectedness of the individual, family, community, and larger systems in preventing STIs, HIV, HCV, and teen pregnancy. Furthermore, CBPR, which has become an established methodological framework for partnering with AI communities to conduct research, has been sparsely applied to understanding and addressing Indigenous SRH. CBPR has the potential to facilitate the

implementation and evaluation of an ecological intervention in AI communities, particularly given its amenability to multi-sectoral and multi-level stakeholder involvement in the research process.

